## 6 STUDY PROCEDURES

### 6.1 Schedule of Assessments

The study flow chart, including all procedures to be performed during the study, is presented below. Prior to engaging in any study procedure, each patient must sign and date an informed consent form. The following schedule of assessments applies to all subjects; assessments that are more frequent should be obtained if clinically indicated. Cycles are scheduled to be 28 days in length.

If the subject is unable to have a study assessment taken within the defined time window due to an event outside of his or her control (e.g., clinic closure, personal emergency, inclement weather, vacation), the assessment should be performed as close as possible to the required schedule.

Cycle = 28 days	Screening	Cycle 1			Cycle 2	Cycle 3	Cycle 4 +	End of Treatment	Survival Follow-Up
	Day -30 to -1	Day 1	Day 14	Day 21 (+ 3 days)	Day 1 (± 3 days)	Day 1 (± 3 days)	Day 1 (± 3 days)	Post-Treatment	
Informed consent	X								
Medical History 	X								
Physical Exam 	X	X			X	X	X	X	
Vital Signs	X	X	X		X	X	X	X	
Demographics	X								
ECOG Performance Status	X	X			X	X	X	X	
ECG	X								
CBC w. differential and platelet count	X	X			X	X	X	X	
Complete Metabolic Panel 	X	X			X	X	X		
LDH	X	X					X 		
Lipase	X	X 					X 		

 Including cancer history, prior therapy including prior radiotherapy, surgical/pathological reports,

 Including height at baseline and weight at each subsequent visit

 Also include direct bilirubin with known Gilbert's syndrome

	Screening	Cycle 1			Cycle 2	Cycle 3	Cycle 4 +	End of Treatment	Survival Follow-Up
	Day -30 to -1	Day 1	Day 14	Day 21 (+ 3 days)	Day 1 (± 3 days)	Day 1 (± 3 days)	Day 1 (± 3 days)	Post-Treatment	
Cycle = 28 days									
UA and UPCR (24-hr urine, if indicated)	X						X 		
PT/INR and PTT	X								
Thyroid function tests (TSH/FT4 initially. If normal, then TSH thereafter)	X						X 	X	
Testosterone	X						X 	X	
Circulating Immune Activity Sample	X	X 					X 	X	
cfDNA 	X	X 					X 	X	
Tumor assessment (CT/MRI a/p, CT chest bone scan)	X						X 	X 	
PSA sample	X	X					X 	X	
Pre-treatment biopsy 	X								
On-treatment biopsy 				X					
Skeletal-related events 	X	X			X	X	X	X	

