 cfDNA, circulating immune activity, lipase can be collected within 30 days prior to C1D1 or pre-dose C1D1

 When plasma DNA is collected, it should be collected as close to biopsy date as possible, including same day. In the event it is collected on the same day, the specimen should be acquired *prior* to the biopsy procedure.

 Every 12 weeks (± 5 days) until disease progression. For EOT, does not have to be repeated if done within 6 weeks of visit.

 Assess continuously until disease progression

 Every 12 weeks beginning with C4D1 (e.g. C4, C7, C10, etc).

 Collect only on C4D1

 Pre-treatment biopsy can be waived provided that adequate archival material for molecular analyses available from biopsy performed within 3 months of enrollment

 On-treatment biopsy during cycle 1 after 3 weeks of therapy. Biopsy must be performed between day 21 and day 24 on therapy (inclusive). *NB: cabozantinib must be held 5 days before and 5 days after biopsy*

Cycle = 28 days	Screening	Cycle 1			Cycle 2	Cycle 3	Cycle 4 +	End of Treatment	Survival Follow-Up
	Day -30 to -1	Day 1	Day 14	Day 21 (+ 3 days)	Day 1 (± 3 days)	Day 1 (± 3 days)	Day 1 (± 3 days)	Post-Treatment	
Concomitant medications 	X	X			X	X	X	X	
Adverse events 	X	X	X		X	X	X	X	
Health Care Resources 	X	X			X	X	X	X	
Cabozantinib dosing 		X			X	X	X		
Dispense/return of oral study drug and compliance accounting		X			X	X	X	X	
Additional cancer treatment, survival status								X	Subjects will be followed every 12 weeks for 2 years after completion of the study or until death, whichever occurs first

 Document those taken from 30 days prior to treatment through 30 days after the decision to discontinue study treatment

 Document new or worsening events from time of informed consent through 30 days after the last dose of study treatment (related SAEs at any time). Adverse events information will be collected at study visits and may also be collected at any time over the phone or by spontaneous subject report. At study visits where any study treatment is administered, adverse events will be documented pre- and post-dose. Certain AEs and all SAEs that are ongoing 30 days after last dose of study treatment are to be followed until resolution or determination by the investigator that the event is table or irreversible.

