## **9 CORRELATIVE/SPECIAL STUDIES**

### *i. Cell-free plasma DNA and archival tissue:*

Plasma samples for ctDNA will be collected for analysis prior to treatment (as close to biopsy timing as possible), at 12 weeks, and at progression using the PC specific platform developed in collaboration with [name]. We will also request archival paraffin embedded tissue to incorporate tissue-based and cell free DNA approaches to assess PC pathway changes and genomic /epigenomic alterations and will correlate with clinical response. We will evaluate the association of molecular biomarkers with treatment response.

We will also compare tumor tissue targeted genomic sequencing results (CLIA test used for inclusion) with ctDNA findings at baseline and determine their concordance, identify and track these alterations, monitor ctDNA tumor content and quantify relevant tumor clones on therapy, and analyze somatic

alterations that emerge at the time of progression/therapy resistance. We predict that a molecularly defined subset of CRPC will preferentially respond to Cabozatinib and this group is detectable using plasma-based assays. These data will help develop a non-invasive blood-based method for future trial inclusion criteria, as well as provide new insights into mechanisms of response/resistance to Cabozantinib in prostate cancer.

ii. *Immune Assays:*

Mandatory collection of 5 mL of plasma or serum in Serum Separation Tubes will be obtained at baseline, every 12 weeks, and at the time of disease progression. These will be aliquoted in 100 microliter fractions and stored at -80 degrees C prior to thaw for analysis.

iii. *Tumor Tissue:*

Metastatic tumor tissue biopsies will be taken with core needle or excisional biopsy. Fine needle aspiration is **not** allowed. It is encouraged that 6 core samples be collected from a single site with a minimum of 4 core samples collected. The biopsy sample will be split into two components, one formalin fixed for histological and immunohistochemical analyses, as well as possible DNA mutation analysis. The other component will be flash frozen for RNA isolation and sequencing. In addition to the typical hematoxylin and eosin staining for tumor morphology and histologic classification.

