### 10.6 Progression-Free Survival

Radiographic progression will be assessed as per PCWG3 criteria. Radiographic progression-free survival (rPFS) is a composite endpoint defined as the time from treatment start to disease progression in bone or soft-tissue, or death, whichever occurs first. All assessments of disease should be collected at the same time interval (e.g., bone scan, CT scan, and PSA). In addition to PSA, confirm post-treatment changes in measurable target lesions, radionuclide bone scans, and symptoms.

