## **12.4 Analysis of Exploratory Endpoints**

Data generated will include IHC scores for targets of cabozantinib, scores for immune cell infiltrate, whole exome sequencing (WES), targeted DNA sequencing, and RNA-Seq for expression. Measures with significant changes from baseline will be determined using the appropriate two-sample test: either a paired t-test or Wilcoxon signed rank test for continuous measures and a chi-square test for categorical variables. The Benjamini-Hochberg procedure will be used to control the false discovery rate for the genomic measurements (DNA, RNA Seq). If the variables are ordinal, an analysis will be done for the proportion of changes that were "positive", "negative", or "no change". An assessment of differences between groups (*e.g.* patients with and without tumor response) will be evaluated with a two-sample t-test or Wilcoxon rank sum test, whichever is most appropriate, for continuous measurement. A chi-square or Fisher's exact test will be used to compare categorical variables between groups of interest. A comparison of time-to-event variable between subgroups of interest will be done with a log-rank test. Associations of variables with time-to-event outcomes will be made with Cox proportional hazard models. For baseline variables the survival clock will start at baseline; for

variables measured later, a landmark analysis will be done starting the survival clock at the time the data were obtained (and removing patients who had the event of interest before that time). We will also perform a Cox regression that treats multiple measurements of a variable as time-dependent

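### In the exploratory rPFS landmark analysis, the Cycle 4 Day 1 blood draw falls inside the first-scan window, so men found progressing at week 12 are kept or dropped by appointment order and a marker of current progression can look predictive.

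*Combined protocol and SAP*

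**What the plan says.** Section 12.4 covers time-to-event outcomes in general: "Associations of variables with time-to-event outcomes will be made with Cox proportional hazard models". Variables measured after baseline get a landmark analysis, "starting the survival clock at the time the data were obtained (and removing patients who had the event of interest before that time"). It gives no fixed landmark day, no rule for an event at the same visit as the sample, and no gap between sample and clock start.

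The timing comes from Section 6.1. "Cycles are scheduled to be 28 days in length", and Cycle 4 Day 1 carries a ± 3 day window. For on-treatment cfDNA the footnote is "Collect only on C4D1" (a further sample is taken at end of treatment). Immune samples and PSA are taken "Every 12 weeks beginning with C4D1". Tumor assessment is "Every 12 weeks (± 5 days) until disease progression". Section 9 likewise places the on-treatment ctDNA sample "at 12 weeks, and at progression using the PC specific platform".

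Section 10.6 asks for near-coincidence: "All assessments of disease should be collected at the same time interval (e.g., bone scan, CT scan, and PSA"). No section says whether blood or scan comes first. Section 10.4 asks for bone progression at the first scheduled assessment to be confirmed on a second scan at least 6 weeks later, unless soft-tissue disease or symptoms have clearly worsened. It does not say which scan dates the event.

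**The concern.** A landmark analysis is meant to separate what is known at the landmark from what happens afterwards. Here the landmark is each man's own draw date, and the scan that reveals whether he has already progressed falls within days of it, on either side. Two men with the same disease and the same marker value are treated differently if one is scanned on Monday and bled on Tuesday, and the other the reverse. The first is excluded. The second contributes an rPFS event almost at time zero, although his disease had in most cases progressed before the blood was taken.

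A marker that only reflects existing progression, as a ctDNA level might, can then be reported as predicting later rPFS. Section 9 hopes the plasma data will help shape inclusion criteria for future trials, so a spurious association could be carried forward.

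**Working it through.** **Inputs.** 28-day cycles, draw at Cycle 4 Day 1 ± 3 days, scan at week 12 ± 5 days (Section 6.1). Historical median rPFS 5.6 months (Section 12). Up to 28 men with liver metastases (Section 12.1), 30 in total (Section 12.2).

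**The plan's own figure.** Section 12.4 states none for this analysis. Section 12 equates a 5.6-month median with about 50% free of rPFS events at 6 months. An exponential model gives 2^(−6/5.6) = 47.6%, which agrees roughly, so the same model is used below.

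**Step 1, windows.** Cycle 4 Day 1 = 1 + 3 × 28 = day 85, so the draw falls on days 82 to 88. Week 12 is day 84 (scan on days 79 to 89) or, counted from Cycle 4 Day 1, day 85 (days 80 to 90). Either scan window contains the whole draw window.

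**Step 2, who is kept.** There are 7 × 11 = 77 pairs of draw and scan days, taken as equally likely.
- Scan on days 79 to 89: scan on or after the draw in 35 of 77 (45%).
- Scan on days 80 to 90: 42 of 77 (55%).
- Draw and scan always on the same day: 100%.

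The earliest draw is day 82 and the latest scan day 89 or 90, so kept events fall at about day 0 to 7 or 8.

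**Step 3, how many men.** Week 12 is 84/30.4375 = 2.76 months. The share with an event by then is 1 − 2^(−2.76/5.6) = 28.9%: 8.1 of 28, or 8.7 of 30. At medians of 4.2, 6.2 and 8.4 months the share is 36.6%, 26.5% and 20.4%. Of the 8.1, about 8.1 × 35/77 = 3.7 to 8.1 × 42/77 = 4.4 stay in with independent dates, and all of them if draw and scan share a day. In simulations with 30 men, the kept cases were 24% (independent dates, days 80 to 90) to 36% (same day) of all post-landmark events.

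**Step 4, effect on the test.** The simulated marker is d SD higher in men already progressed at the draw and unrelated to later risk. The true association with later rPFS is therefore nil. Rejection rates of a two-sided 5% Cox test at a 5.6-month median:

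| Timing of draw and scan | d = 0.5 | d = 1.0 | d = 1.5 |
|---|---|---|---|
| 28 men, independent, scan days 79 to 89 | 7–8% | 13–15% | 24% |
| 30 men, independent, scan days 80 to 90 | 8% | 17% | 31% |
| 30 men, same day | 8% | 23% | 42% |
| 30 men, scan 0 to 2 days after draw | 11% | 29% | 52% |

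The ranges in the first row come from separate simulation runs. With d = 0 the rate is 4–5%. With 30 men, d = 1 and independent dates, it is 20%, 16% and 13% at medians of 4.2, 6.2 and 8.4 months. Removing every man whose progression is on the first scan returns the rate to 4–6% throughout. When scans keep to their window, a day-91 landmark removes the same men.

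**The case against.** The strongest reply is that this is one word in an exploratory section. No decision, error rate or sample size hangs on it. Section 12.4 names neither rPFS nor any week-12 variable, and it also plans baseline-clock Cox models, responder comparisons and a time-dependent Cox model. The cytokine hypotheses in Section 2.5 concern change from baseline. All of this stands. A reader might infer that the landmark fit is the trial's designated test of week-12 ctDNA and cytokines; the documents do not say so.

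The scope is also narrower than it first appears. For OS the event is death, so a scan in the same week is irrelevant and the rule already keeps every man alive at the draw. The day 21 to 24 biopsy is far from any scheduled scan.

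Bone disease complicates the mechanism. If confirmed bone progression is dated to the second scan, those men stay in whatever the order, with events about six weeks or more later. The day 0 to 8 pattern then describes soft-tissue progression, and describes bone only if the first scan dates the event.

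The size rests on assumptions: marker shift, exponential rPFS, and independent uniform dates, which sit uneasily with Section 10.6. Deaths and unscheduled scans before week 12 would lower the number of first-scan cases. At a 0.5 SD shift the inflation is small. None of this removes the dependence of membership on appointment order, which follows from the text alone.

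**Conclusion.** The point holds for exploratory rPFS associations of the Cycle 4 Day 1 blood variables (cfDNA, immune samples, PSA). As written, about 4 of 28 men (independent dates) to 8 (same day) would be counted as later events when their progression was found at the week-12 assessment.

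The false-positive rate depends on how strongly the marker tracks current progression, which the documents do not give. Over an assumed 0.5 to 1.5 SD it is roughly 7% to 24% with independent dates and scan days 79 to 89, and up to 31% with days 80 to 90. Same-day scheduling raises it further at 1.0 and 1.5 SD. These are illustrations of a possible bias, and do not show that any particular marker will mislead.

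A reader might infer that the primary result is compromised. It is not: the Kaplan-Meier estimate in Section 12.3.1 runs from treatment start and uses no landmark. The change is worth making because it is cheap and the stated rule defeats the purpose of landmarking for these samples.

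**What to change.** In Section 12.4, for Cycle 4 Day 1 variables and rPFS:

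- Use one common landmark after the first-scan window closes, at day 91 or later. Day 90 can still lie inside the window.
- Exclude men whose progression is dated at or before that landmark; deaths by then drop out as now.
- State that confirmed bone progression is dated to the first scan that showed it. Because confirmation comes after the landmark, add a sensitivity analysis that also drops men with unconfirmed new bone lesions on that scan.
- Keep progression on a first scan done late, after the landmark, as a post-landmark event, with a sensitivity analysis excluding it.

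Leave the OS landmark analysis as it is.

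The cost is a few sentences of analysis text, with no change to visits, samples or treatment. The analysis loses about 4 to 8 men. All are events, so precision in an already small exploratory analysis falls by more than the head count suggests.

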## **12.5 Reporting and Exclusions**

### ***12.5.1 Evaluation of Toxicity***

All subjects will be evaluable for toxicity from the time of their first treatment with cabozantinib provided they have had at least 4 weeks of drug.

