	
tumor immune microenvironment response through on-treatment biopsy, ideally of same pre-treatment site, and collection of plasma for analysis
 
 
○ To explore any relationship between baseline and on-treatment tumor genomic alterations (such as mutations, translocations, messenger ribonucleic acid [mRNA], protein expression and localization) with any observed antitumor activity
 

Endpoints	
Radiographic progression free survival, response rate (radiographic RR, ≥50% PSA response rate, overall survival, and adverse event rate

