**NOTE: Cabozantinib must be held 5 days before and 5 days after biopsy**

#### **6.6 Cycle 2, Day 1 + Cycle 3, Day 1**

- Physical Examination with vital signs and weight
- ECOG Performance Status
- CBC with differential and platelet count
- CMP (with direct bilirubin with known Gilbert's syndrome)
- Concomitant medications
- Skeletal-related events
- Adverse events
- Dispense/return oral study drug and compliance accounting

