### **7.9.2 Cabozantinib**

The most frequent AEs experienced by  $\geq 20\%$  of subjects treated with cabozantinib in descending order of frequency were diarrhea, fatigue, decreased appetite, nausea, weight decreased, PPES, vomiting, constipation, hypertension, dysgeusia, dysphonia, asthenia, and dyspnea. For a full description of the safety profile of cabozantinib, refer to the cabozantinib Investigator's Brochure.

Other medically important but less frequent AEs including arterial thrombotic AEs (e.g. transient ischemic attack [TIA], and myocardial infarction [MI]) and venous thrombotic AEs (e.g. deep vein thrombosis [DVT] and pulmonary embolism), severe hemorrhagic events, proteinuria, wound healing complications, gastrointestinal (GI) perforation, abscesses including intra-abdominal and pelvic abscess, GI and non-GI fistula formation, osteonecrosis, and reversible posterior leukoencephalopathy syndrome (RPLS).

Adverse events associated with laboratory abnormalities experienced by  $\geq 5\%$  of subjects treated with cabozantinib in descending order of frequency were anemia, AST increased, ALT increased, hypothyroidism, hypokalemia, hypomagnesemia, thrombocytopenia, hypocalcemia, hypophosphatemia, lactate dehydrogenase (LDH) increased, lipase increased, neutropenia, hyponatremia, ALP increased, leukopenia, and hyperglycemia.

Adverse events may occur within the first few weeks in the course of treatment with cabozantinib, as cabozantinib is expected to reach steady state exposure at approximately 2 weeks following first dose. Events that generally have an early onset include hypocalcemia, hypokalemia, thrombocytopenia, hypertension, PPES, abdominal pain, mucosal inflammation, constipation, diarrhea, and vomiting.

Adverse events should be managed with supportive care at the earliest signs of toxicity. Dose reductions and treatment interruptions should be considered. Dose reductions are recommended for events that, if persistent, could become serious or intolerable (See Table 7.2).

Cabozantinib should be discontinued for the following AEs: visceral perforation or fistula formation, severe hemorrhage, serious arterial thromboembolic events, nephrotic syndrome, hypertensive emergency, persistent uncontrolled hypertension despite optimal medical management, and RPLS.

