## **12.2 Sample Size/Accrual Rate**

Sample size for the entire trial will be 30 patients. Accrual will not mandate an equal number of each of the qualifying molecular abnormalities. The sponsor retains the right to terminate enrollment in any specific genetic alteration if no significant benefit is observed in that given cohort.

Any enrolled subject who withdraws for any reason prior to a full 28 days of treatment and assuming he did undergo the second biopsy ("on treatment biopsy") will be replaced and not incorporated into the analysis.

Accrual is anticipated to be 1-4 patients per month in total across all study sites

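### The planned toxicity summary counts only patients with at least 4 weeks of drug, so those who stop earlier because of toxicity drop out of it

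*Combined protocol and SAP*

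**What the plan says.** Section 12.5.1, under the heading on reporting and exclusions, makes subjects "evaluable for toxicity from the time of their first treatment with cabozantinib provided they have had at least 4 weeks of drug". Section 12 defines no other safety population. The synopsis (Section 1) lists among the endpoints "overall survival, and adverse event rate", so Section 12.5.1 is the only text that sets the denominator for that rate.

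Section 12.2 adds that a subject who "withdraws for any reason prior to a full 28 days of treatment and assuming he did undergo the second biopsy" "will be replaced and not incorporated into the analysis". It does not say whether the analysis meant is efficacy, safety or both.

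On timing, Section 7.9.2 says "Adverse events may occur within the first few weeks in the course of treatment with cabozantinib", puts steady state at about 2 weeks, and lists events with early onset. On collection, there is no exposure minimum. Footnote 13 to the schedule in Section 6.1 reads "Document new or worsening events from time of informed consent through 30 days after the last dose of study treatment".

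**The concern.** Membership of the toxicity set depends on having stayed on drug for 4 weeks, which is itself affected by toxicity. Section 7.9.2 requires cabozantinib to be discontinued for several severe events. A patient who has one of these in week 2 and stops as directed is not evaluable for toxicity under Section 12.5.1. A report that follows the rule would show no treatment-ending toxicity in the first 4 weeks, whatever happened. In a single-arm trial of 30, a few missing patients change the reported rates visibly, and readers would take those rates as the tolerability of the drug in this population.

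**Working it through.** The plan states no figure for this point, so there is none to reproduce. The check has four parts.

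**1. How many patients could be lost.** Section 12.2 gives the size: "Sample size for the entire trial will be 30 patients". The documents give no rate p of stopping for toxicity before 4 weeks, so p is an assumption, taken from 3% to 20%. The expected loss is 30p, and the chance of losing at least one patient is 1 − (1 − p)^30.

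| p (assumed) | Expected lost of 30 | Chance of losing at least one |
|---|---|---|
| 3% | 0.9 | 60% |
| 5% | 1.5 | 79% |
| 10% | 3.0 | 96% |
| 20% | 6.0 | 99.9% |

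**2. Effect on a severe-event rate.** Let n patients be treated. Of these, k stop before 4 weeks, and j of those k had a severe event. Let m patients who stayed on have a severe event. The all-treated rate is (j + m)/n and the rate under Section 12.5.1 is m/(n − k). The first is a weighted average of j/k and m/(n − k). The rule therefore understates the rate exactly when severe events are more common among early stoppers than among those who stay.

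Illustrations with n = 30 (event counts are assumptions):
- k = j = 3, m = 3: all treated 6/30 = 20.0% (exact 95% CI 7.7% to 38.6%); under the rule 3/27 = 11.1% (2.4% to 29.2%).
- The same case, with the 3 replaced by patients without the event: reported 3/30 = 10.0%, against 6/33 = 18.2% of everyone treated.
- k = j from 1 to 6, m = 3: all treated from 4/30 = 13.3% to 9/30 = 30.0%; under the rule from 3/29 = 10.3% to 3/24 = 12.5%.
- k = 3 stopping for other reasons (j = 0), m = 6: all treated 6/30 = 20.0%; under the rule 6/27 = 22.2%. Here the rule overstates the rate.

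For toxicity that ends treatment before 4 weeks, the rule reports 0% in every case. With 3 such patients the true figure is 3/30 = 10%.

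**3. What 4 weeks of drug means.** The note to Section 6.5 says "Cabozantinib must be held 5 days before and 5 days after biopsy", and the biopsy falls on days 21 to 24. With the biopsy day also held, 11 days are lost. A day-21 biopsy leaves doses on days 1–15 and 27–28, which is 17 by day 28. A day-24 biopsy leaves days 1–18, which is 18. The 28th dose falls on day 28 + 11 = 39. If drug is taken on the biopsy day, the counts are 18 to 19 and the 28th dose falls on day 38. Against a dosing-day reading, Section 6.5 itself describes days 21 to 24 as 3 weeks of therapy although drug has been held for the 5 days before. The protocol thus appears to count treatment time by calendar, and Section 12.2 speaks of days of treatment in the same way. The wording is ambiguous, and usage favours about day 28.

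**4. Whether another section restores these patients.** Sections 6.1, 11.1, 13.1.2, 13.1.5 and 14 cover recording, data capture, reporting and monitoring. None of them defines an analysis set or returns early stoppers to the toxicity summary.

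**The case against.** A reader might infer that early stoppers disappear from the safety results altogether. The documents do not support that. Adverse events are recorded from consent (Sections 6.1 and 13.1.2), data are captured for all enrolled subjects (Section 11.1), serious events are reported from the start of drug (Section 13.1.5), the monitoring board receives an adverse event table and immediate reports (Section 14), and the medical monitor reviews all serious events and deaths (Section 14.1). Only the evaluable-for-toxicity summary is restricted.

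A reader might also infer that everyone stopping in the first 5.5 weeks is excluded. The dose count behind this is correct, but the protocol's usage favours calendar time, so it is a point to clarify and not a further harm.

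Nor does early onset mean exclusion. A patient with an early event who stays on past 4 weeks is counted from first dose, and Section 7.8.1 manages most events by supportive care, interruption or reduction. Downward bias is likewise not certain for every rate, as the last illustration in the working shows.

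Finally, safety is not a stated objective in Section 1.2 or an endpoint in Section 12.1, and the primary analysis does not depend on Section 12.5.1.

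All of this stands as a limit on the point. It does not remove it: the one safety set that the plan defines still excludes patients who could not tolerate 4 weeks of drug.

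**Conclusion.** The rule is wrong as written and should be changed. For toxicity that ends treatment before about day 28, the planned summary gives zero by construction, with no assumption needed. For severe-event rates overall, understatement follows if early stops are mainly for toxicity. Its size depends on an early-stop rate that the documents do not give: about 1 to 6 of 30 patients lost if that rate is 3% to 20%. The effect is confined to the toxicity summary.

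Section 12.2 is part of the same problem. Taken literally, its biopsy condition covers only those who withdrew after the second biopsy, and it leaves open how earlier withdrawals are treated. Left alone, it would conflict with a corrected Section 12.5.1.

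**What to change.** - **Section 12.5.1:** delete the 4-week proviso and write: *All subjects who receive at least one dose of cabozantinib are evaluable for toxicity from first dose.* This also removes the calendar-or-dosing-days question for the safety set.
- **Section 12.2:** state that replaced subjects stay in the safety set, so that its denominator is everyone treated and may exceed 30. Clarify the biopsy condition and which analysis the exclusion refers to.
- **Adverse event window:** reconcile its end. Section 6.1 counts 30 days from the last dose, while Sections 13.1.2 and 13.1.5 count 30 days from the decision to discontinue. Related serious events are collected at any time (Sections 6.1 and 13.1.5), and the safety summary should say how they are shown.

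The cost is a sentence or two. The data are already collected, so no new procedures are needed. Reported adverse event rates may look slightly less favourable.
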